 - The refractory nonremitting disease subject has no remission since the diagnosis of disease as per clinical expectations. Thus, the subject has documentation of prior diagnosis of GCA as per above Diagnostic Criteria > 6 weeks before Day 0; however, presence of Acute Phase Reactants and Signs/Symptoms as per above persists within 6 weeks of Day 0.

Subjects who complete screening procedures and are not considered eligible (screen failures) may be rescreened one time provided there is reason to believe that eligibility criteria will be met.

Stratified eligible subjects will enter the double-blind treatment period after randomization 3:2 to blinded treatment with KPL-301 150 mg or placebo administered SC every other week (every 2 weeks). All subjects will also receive an unblinded 26-week oral prednisone taper according to a standardized tapering protocol.

Prior to first administration of KPL-301 or placebo, all subjects are required to achieve remission (i.e., resolution of GCA symptom(s) and CRP < 1.0 mg/dL or ESR < 20 mm in the first hour). Should a subject in screening not achieve remission by > 6 weeks of onset they can be rescreened using their prior flare documentation following the relapsing/refractory non-remitting inclusion criteria.

The first administration of subcutaneous KPL-301/placebo and oral prednisone taper will take place at the study site on Day 0. Subsequent doses of KPL-301/placebo will be administered at the study site in conjunction with a scheduled study visit or administered by the subject on an outpatient basis in accordance to the dosing schedule. The oral steroid taper will be self-administered by study subjects on a daily basis.

Subjects will be followed at the study site at Weeks 1, 2, 3, 4, and approximately every 4 weeks thereafter (see Table 1). Subjects reporting worsening of GCA symptoms or any safety issues may be brought in for an unscheduled visit at the study site at any time.

If a flare/relapse is suspected, the Investigator must consult the Contract Research Organization (CRO)-designated Medical Expert to review and harmonize the elements of the diagnostic work-up.

Flare/relapse is defined as a re-increase of CRP from normal to 1 mg/dL or greater and/or of ESR from less than 20 mm in the first hour to 30 mm or greater AND at least one of the following signs or symptoms attributed by the Investigator to new, worsening, or recurrent GCA:

- Cranial symptoms

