8.7 Eligibility Criteria

8.7.1 Inclusion Criteria

To be eligible to participate in the trial, a subject must meet all of the following criteria:

Inclusion Criteria

1. Able and willing to provide written informed consent and to comply with the study protocol
2. Age of ≥ 50 to 85 inclusive

3. Diagnosis of new-onset or relapsing GCA classified according to the following criteria:

New-onset: Initial diagnosis of GCA within 6 weeks of Day 0

- a) Westergren ESR > 30 mm/hour or CRP \geq 1 mg/dL
- b) AND at least one of the following:
 - i. Unequivocal cranial symptoms of GCA (new-onset localized headache, scalp or temporal artery pain or tenderness, ischemia-related vision loss, or otherwise unexplained mouth or jaw pain upon mastication)
 - ii. Unequivocal extracranial symptoms of GCA such as claudication of the extremities
 - iii. Symptoms of PMR, defined as shoulder and/or hip girdle pain associated with inflammatory morning stiffness
- c) AND at least one of the following:
 - i. TAB or ultrasound revealing features of GCA
 - ii. Evidence of large-vessel vasculitis by angiography or cross-sectional imaging study such as MRI, CT/CTA, or PET-CT of the aorta or other great vessels

Relapsing: Diagnosis of GCA > 6 weeks before Day 0 AND

Active GCA within 6 weeks of Day 0 defined as clinical sign/symptom(s) and Westergren ESR > 30 mm/hour or CRP \geq 1 mg/ dL

Refractory nonremitting: Diagnosis of GCA > 6 weeks before Day 0 AND

No remission since the diagnosis of disease as per clinical expectations i.e. Presence of sign/symptoms as per above and Westergren ESR > 30mm/hour or CRP \geq 1 mg/dL within 6 weeks of Day 0

4. Remission of GCA at or before Day 0 (resolution of GCA symptom(s) and CRP < 1.0 mg/dL or ESR < 20 mm in the first hour), such that the subject can safely participate in the study and follow the protocol defined procedures, including initiation of the prednisone taper at the protocol-specified starting dose (i.e., \leq 60 mg/day)
 5. At Day 0, receiving or able to receive oral prednisone up to 60 mg/day for the treatment of active GCA
 6. If using MTX, oral or parenteral up to 25mg/week is permitted during screening if started more than 6 weeks prior to Day 0 and should be tapered to zero by Day 0.
 7. Willing to receive antiplatelet therapy depending on the Investigator's decision
 8. Willing to receive treatment for prevention of corticosteroid-induced osteopenia/osteoporosis depending on the Investigator's decision

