### **5.1.3. Baseline Values**

For purpose of analyses, a baseline is defined as the last non-missing value obtained prior to the start of study treatment. For CRP and ESR, a baseline should be within 3 days of study treatment.

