### 6.7.3. Analysis of Secondary Efficacy Endpoints

All analyses of secondary efficacy endpoints will use the mITT population. Sustained remission rate will be based on the adjudication outcome. Local assessments of ESR, CRP, and imaging will be used for other secondary efficacy endpoints.

#### 6.7.3.1. Sustained remission rate at Week 26

Subjects who complete the treatment period without a flare by week 26 will be considered to have sustained remission. The sustained remission rate at week 26 can be obtained from the estimates of time to flare at week 26 by using the Kaplan-Meier method, along with their standard errors using Greenwood's formula. Comparison with p-value will be conducted between the treatment groups. Two-sided p-value and 95% CI calculated using normal approximation.

#### 6.7.3.2. Time to elevated ESR by week 26

Time to elevated ESR will be defined as the time from randomization to earliest date of an ESR value of  $\geq 30$  mm/hr. All subjects who do not have an elevated ESR by week 26/ EOT will be censored at last assessment date or the randomization date, whichever is later.

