**Table 2: Censoring Rules for Time to Elevated ESR by Week 26**

	Scenario	Event or Censoring	Date of Event or Censoring
1	Elevated ESR on or prior to week 26	Event	Date of elevated ESR
2	No elevated ESR on or prior to week 26	Censored	Date of last assessment with no elevated ESR by week 26
3	No elevated ESR on or prior to EOT	Censored	Date of last assessment with no elevated ESR by EOT
4	No post baseline assessment	Censored	Date of randomization

Analysis and presentation will be the same as that of the primary efficacy endpoint. The KM method to estimate the survival functions for each treatment group (overall and by stratification factor). The treatment comparison will be based on a stratified log-rank test. The Hazard ratio (HR) and its 95%

CI will be estimated using a stratified Cox model with treatment as the explanatory variable and strata as the stratification factor.

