#### **6.7.3.3. *Time to elevated CRP by week 26***

Time to elevated CRP will be defined as the time from randomization to earliest date of a CRP value of  $\geq 1.0$  mg/dL. All subjects who do not have an elevated CRP by week 26/ EOT will be censored at last assessment date or the randomization date, whichever is later. Detailed censoring rule follows that for ESR. Subjects with elevated CRP at baseline will be excluded from the analysis.

Analysis and presentation will be the same as that of the primary efficacy endpoint. The KM method to estimate the survival functions for each treatment group (overall and by stratification factor). The treatment comparison will be based on a stratified log-rank test. The HR and its 95% CI will be estimated using a stratified Cox model with treatment as the explanatory variable and strata as the stratification factor.

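### Time to elevated ESR has no baseline condition, so an ESR that was already raised at entry counts as a new event, although the matching CRP endpoint excludes such subjects

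*SAP*

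**What the plan says.** SAP 6.7.3.2 reads: "Time to elevated ESR will be defined as the time from randomization to earliest date of an ESR value" of 30 mm/hr or more. In Table 2 the event row is "Elevated ESR on or prior to week 26", with no lower limit in time and no row for a subject whose ESR was raised before treatment. The last row, "No post baseline assessment", censors at randomization, which implies that a post-baseline value is needed.

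SAP 6.7.3.3 builds the CRP endpoint the same way. It says "Detailed censoring rule follows that for ESR" and then adds a sentence that has no ESR counterpart: "Subjects with elevated CRP at baseline will be excluded from the analysis".

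Protocol 8.7.1, inclusion criterion 4, defines remission as "resolution of GCA symptom(s) and CRP < 1.0 mg/dL or ESR < 20 mm in the first hour". One normal marker is enough. SAP 5.1.3 provides the value needed for a baseline rule: "For CRP and ESR, a baseline should be within 3 days of study treatment". SAP 7.1, which lists changes from the protocol, does not mention the difference between the two markers.

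**The concern.** A subject whose CRP has settled can be randomized with ESR still at 30 mm/hr or more. ESR is measured again at Week 1. If it has not yet come down, the rule records an event at that visit even though nothing has risen. The protocol's flare definition (8.4.1) describes the ESR component as a change "of ESR from less than 20 mm in the first hour to 30 mm or greater", which is a rise from normal.

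The ESR result would then combine two things, ESR that has not normalized and ESR that has gone up again. It would not answer the same question as the CRP result beside it. Early events that are equally common in both arms pull the hazard ratio toward 1.

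The position in the testing order gives this weight. Time to elevated ESR is second of the nine ordered secondary endpoints in SAP 3.2 and the third test counting the primary. Testing stops at the first non-significant result (SAP 6.7.1), so a diluted ESR result would block 9 − 2 = 7 later endpoints, including CRP and cumulative steroid dose.

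**Working it through.** **Can the case arise, and is it handled elsewhere?** Criterion 4 joins the two markers with an or, so ESR ≥ 30 with CRP < 1.0 mg/dL is eligible. The same or admits a raised CRP, which SAP 6.7.3.3 does handle. No other section of either document supplies an ESR condition.

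**The plan's own power figure (time to flare).** SAP 1.3 assumes 85% vs 50% flare-free at Week 26.
- HR = ln(0.85)/ln(0.50) = 0.234.
- Expected events = 42 × 0.15 + 28 × 0.50 = 20.3.
- Schoenfeld, 20 events, 3:2: Φ(√(20 × 0.6 × 0.4) × |ln 0.234| − 1.96) = Φ(3.18 − 1.96) = 0.89.
- Freedman, k = 1.5: Φ(√(20 × 1.5) × (1 − 0.234)/(1 + 1.5 × 0.234) − 1.96) = Φ(3.11 − 1.96) = 0.874, which matches the stated 87%.

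That figure concerns flare and is not in question. The documents give no power for time to elevated ESR.

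**Illustration for ESR.** Let f be the share with baseline ESR ≥ 30. Assumptions not in the documents:
- ESR event rates equal the flare rates.
- f is the same in both arms.
- A stated fraction of the raised subjects is still raised at Week 1 and becomes an event there.
- The other raised subjects then have the same hazard as everyone else.

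The test is a stratified log-rank with two strata of 21 vs 14, exponential times, and events read at Weeks 1–4, 8, 12, 16, 20, 24 and 26. There were 4,000 runs per cell. Power with no subject raised at baseline is 0.90.

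| f | As written, all persist | Half | Quarter | With exclusion |
|---|---|---|---|---|
| 10% | 0.76 | 0.82 | 0.86 | 0.87 |
| 20% | 0.60 | 0.74 | 0.82 | 0.83 |
| 30% | 0.48 | 0.67 | 0.79 | 0.77 |

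Repeat simulations agreed to within about 0.03.

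- **Hazard ratio (large-sample Cox limit), all / half / quarter persisting:** from 0.23 to 0.35 / 0.29 / 0.26 at f = 10%, and to 0.47 / 0.36 / 0.30 at f = 20%.
- **Make-up of events at f = 20%, full persistence:** 70 × 0.20 = 14 persistent, plus 0.80 × 20.3 = 16.2 new, about 30 in all. Nearly half are not new rises.
- **Higher event rates (75% vs 30% event-free):** at f = 10%, 0.91 / 0.95 / 0.97 as written against 0.96 with exclusion; at f = 20%, 0.81 / 0.92 / 0.96 against 0.94.
- **Persistence 50% on drug vs 100% on placebo, f = 20%:** 0.88 as written, against 0.83 with exclusion.
- **Null check (f = 20%, full persistence, equal arms):** two-sided rejection 0.052.

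**The case against.** The strongest reply is that the power loss rests on unknowns and may not occur. Laboratory elevation without symptoms may be commoner than flare, and at the higher event rates the loss is small unless nearly all raised values persist. Protocol 6.3 reports that the drug lowered ESR in rheumatoid arthritis, so persistence could be lower on drug. At f = 20%, persistence of 30% vs 50% gives 0.85 as written against 0.83 with exclusion, although 75% vs 100% gives 0.76 against 0.83. All of this stands: the direction of the power effect is not known.

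It is also fair that the SAP's own flare definition (6.7.2) is level-based and that the protocol names this endpoint only as elevated ESR. The protocol's flare wording is therefore supporting evidence and not a rule for this endpoint. Excluding at 30 or more does not reproduce that wording either, since subjects at 20–29 stay in; it reproduces the CRP rule. Flare under 6.7.2, however, also needs signs, symptoms or imaging and is adjudicated. The ESR endpoint has neither safeguard.

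Exclusion also departs from the mITT set named in 6.7.3. The CRP analysis already does so, and because the baseline value precedes treatment, the randomized comparison among the remaining subjects is kept. The alternative of keeping everyone and requiring a value below 30 before an event can count makes the start of risk depend on a post-randomization outcome that treatment may affect.

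None of this explains why ESR and CRP are treated differently.

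**Conclusion.** The concern holds. As written, the rule records persistent ESR elevation as a new event, and it conflicts with the plan's own handling of CRP. That conclusion rests on the text and needs no assumption about rates.

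The consequence for power is conditional on f, on persistence and on ESR event rates, none of which is documented. Full persistence in both arms gives the largest loss: about 11 points relative to exclusion at f = 10% (0.87 − 0.76) and 23 points at f = 20% (0.83 − 0.60). At quarter persistence there is almost no difference. If the drug speeds normalization, the written rule can have more power, but the result then partly measures resolution and not re-elevation. The primary endpoint and type I error are not affected. The change should be made; it does not threaten the trial's main conclusion.

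**What to change.** In SAP 6.7.3.2, state that subjects whose baseline ESR is 30 mm/hr or more are left out of this analysis and that only values after baseline can be events. The second part also settles a Day 0 reading, since ESR is scheduled on the day of randomization. Report the number excluded in each arm.

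State one rule, the same for ESR and CRP, for a subject with no baseline value inside the 3-day limit of SAP 5.1.3. Keeping such subjects in is simplest but may readmit a few raised values; leaving them out loses a few more subjects. Either is workable if fixed before unblinding.

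The cost is two or three sentences. Baseline ESR is already collected and summarized (SAP 6.3). The ESR set becomes slightly smaller than mITT, as the CRP set already is. If few raised values persist, the gain is in interpretation and not in power.

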**Table 2: Censoring Rules for Time to Elevated ESR by Week 26**

	Scenario	Event or Censoring	Date of Event or Censoring
1	Elevated ESR on or prior to week 26	Event	Date of elevated ESR
2	No elevated ESR on or prior to week 26	Censored	Date of last assessment with no elevated ESR by week 26
3	No elevated ESR on or prior to EOT	Censored	Date of last assessment with no elevated ESR by EOT
4	No post baseline assessment	Censored	Date of randomization

Analysis and presentation will be the same as that of the primary efficacy endpoint. The KM method to estimate the survival functions for each treatment group (overall and by stratification factor). The treatment comparison will be based on a stratified log-rank test. The Hazard ratio (HR) and its 95%

CI will be estimated using a stratified Cox model with treatment as the explanatory variable and strata as the stratification factor.

#### **6.7.3.3. *Time to elevated CRP by week 26***

Time to elevated CRP will be defined as the time from randomization to earliest date of a CRP value of  $\geq 1.0$  mg/dL. All subjects who do not have an elevated CRP by week 26/ EOT will be censored at last assessment date or the randomization date, whichever is later. Detailed censoring rule follows that for ESR. Subjects with elevated CRP at baseline will be excluded from the analysis.

Analysis and presentation will be the same as that of the primary efficacy endpoint. The KM method to estimate the survival functions for each treatment group (overall and by stratification factor). The treatment comparison will be based on a stratified log-rank test. The HR and its 95% CI will be estimated using a stratified Cox model with treatment as the explanatory variable and strata as the stratification factor.

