- c) AND at least one of the following:

- i. TAB or ultrasound revealing features of GCA
- ii. Evidence of large-vessel vasculitis by angiography or cross-sectional imaging study such as MRI, CT/CTA, or PET-CT of the aorta or other great vessels

Relapsing: Diagnosis of GCA > 6 weeks before Day 0 AND:

Active GCA within 6 weeks of Day 0 defined as clinical sign/symptom(s) as per above and Westergren ESR > 30 mm/hour or CRP \geq 1 mg/ dL

Refractory nonremitting: Diagnosis of GCA > 6 weeks before Day 0 AND:

No remission since the diagnosis of disease as per clinical expectations. i.e. Presence of sign/symptoms as per above and Westergren ESR > 30 mm/hour or CRP \geq 1 mg/ dL within 6 weeks of Day 0.

4. Remission of GCA at or before Day 0 (resolution of GCA symptom(s) and CRP < 1.0 mg/dL or ESR < 20 mm in the first hour), such that the subject can safely participate in the study and follow the protocol-defined procedures, including initiation of the prednisone taper at the protocol-specified starting dose (i.e., \leq 60 mg/day)
5. At Day 0, receiving or able to receive oral prednisone up to 60 mg/day for the treatment of GCA
6. If using methotrexate (MTX), oral or parenteral up to 25mg/week is permitted in screening if started more than 6 weeks prior to Day 0 and should be tapered to zero by Day 0
7. Willing to receive antiplatelet therapy depending on the Investigator's decision
8. Willing to receive treatment for prevention of corticosteroid-induced osteopenia/osteoporosis depending on the Investigator's decision
9. Female subjects must be:
 - a) postmenopausal, defined as at least 12 months post cessation of menses (without an alternative medical cause), or
 - b) permanently sterile following documented hysterectomy, bilateral salpingectomy, bilateral oophorectomy, or tubal ligation or having a male partner with vasectomy as affirmed by the subject, or
 - c) nonpregnant, nonlactating, and if sexually active having agreed to use a highly effective method of contraception (i.e., hormonal contraceptives associated with inhibition of ovulation or intrauterine device [IUD], or intrauterine hormone-releasing system [IUS], or sexual abstinence) from Screening Visit until the Final Washout Safety Follow-up visit 84 ± 3 days from EOT Visit.

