### **3.2. Secondary Efficacy Endpoints**

The hierarchical order of the secondary efficacy endpoints are as follows:

- Sustained remission rate at Week 26
- Time to elevated ESR by Week 26
- Time to elevated CRP by Week 26
- Time to signs/symptoms of GCA or new or worsening vasculitis on imaging by Week 26
- Cumulative steroid dose at Week 26
- Percentage of subjects who have completed the corticosteroid taper and who have a normal ESR by Week 26
- Percentage of subjects who have completed the corticosteroid taper and who have a normal CRP by Week 26

- Percentage of subjects who completed the corticosteroid taper and who have neither signs/symptoms of GCA nor new or worsening vasculitis on imaging by Week 26
- Cumulative steroid dose at the end of the Washout Safety Follow-up period

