### **6.3. Demographics and Baseline Disease Characteristics and History**

Demographic and other baseline characteristics will be summarized by descriptive statistics for each treatment group and overall for the SAF. They will also be presented in by-subject listings.

Descriptive statistics will be provided for the following:

- age
- weight (kg)
- height (cm)
- body mass index (BMI) (kg/m^2)

Frequency tabulations will be presented as collected in the eCRF for:

- age (< 65 years or ≥ 65 years)
- sex
- race
- ethnicity
- substance use (tobacco) history (cigarettes, cigars, pipes, or chewing tobacco).

Disease history such as disease status (new-onset or relapsing/refractory), prior GCA (yes/no), biopsy (yes/no), imaging (yes/no), and prior treatment will be summarized using frequencies and percentages and presented in by-subject listings. Time since diagnosis to randomization (month), ESR value for eligibility and at baseline, and CRP value for eligibility and at baseline (local and central separately) will be summarized by descriptive statistics.

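### The gated tests for time to elevated ESR and CRP do not use the subject's baseline marker level as a covariate, and for ESR subjects already at or above 30 mm/hr are not excluded either

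*SAP*

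**What the plan says.** SAP 3.2 fixes the testing order ("The hierarchical order of the secondary efficacy endpoints are as follows"). Of nine secondary endpoints, time to elevated ESR is second and time to elevated CRP third. Under SAP 6.7.1 each test is two-sided at 0.05, and testing ends at the first non-significant result.

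The events are a first ESR of at least 30 mm/hr (SAP 6.7.3.2) and a first CRP of at least 1.0 mg/dL (SAP 6.7.3.3). For ESR, "Analysis and presentation will be the same as that of the primary efficacy endpoint". For CRP, the p-value that passes or fails the gate is described thus: "The treatment comparison will be based on a stratified log-rank test". The hazard ratio follows separately: "The HR and its 95% CI will be estimated using a stratified Cox model with treatment as the explanatory variable". Disease status is the only stratifier.

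Baseline values exist. SAP 5.1.3 says "For CRP and ESR, a baseline should be within 3 days of study treatment", and SAP 6.3 lists "ESR value for eligibility and at baseline, and CRP value for eligibility and at baseline (local and central separately") among the summaries. Only CRP has a rule that uses its baseline: "Subjects with elevated CRP at baseline will be excluded from the analysis". SAP 6.7.3.2 has no counterpart for ESR.

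Inclusion criterion 4 (Protocol Synopsis and 8.7.1) defines remission as "resolution of GCA symptom(s) and CRP < 1.0 mg/dL or ESR < 20 mm in the first hour". Either marker is enough.

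**The concern.** When the event is a marker crossing a fixed line, distance from the line at the start is an obvious candidate predictor. A subject entering with CRP 0.9 mg/dL has less far to go than one entering at 0.1. If the starting level is prognostic, leaving it out of a time-to-event comparison costs power, and two-level disease status does not measure it.

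For ESR the gap is wider. A subject can qualify on CRP while ESR is still 30 or more. Such a subject may have an event almost at once in either arm, which says nothing about the drug and dilutes the comparison.

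The position in the sequence raises the stakes. A miss on ESR or CRP ends formal testing of everything below, including cumulative steroid dose at Week 26 (fifth), which has its own secondary objective in SAP 1.1.2. The SAP already accepts the principle elsewhere: SAP 6.7.3.5 adjusts cumulative steroid dose for the corticosteroid starting dose.

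**Working it through.** **The plan's own figure.** No power is stated for ESR or CRP. The primary endpoint's figure (SAP 1.3) reproduces:
- HR = ln(0.85)/ln(0.50) = 0.2345; medians 26 and 110.9 weeks.
- Expected events = 28 × 0.50 + 42 × 0.15 = 20.3.
- Freedman, 3:2: z = √(20 × 1.5) × (1 − 0.234)/(1 + 1.5 × 0.234) − 1.96 = 1.15, power 87.4% (stated: 87%). Schoenfeld gives 88.9%.

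**Adding the baseline marker.** From the documents: 42 and 28 subjects, two equal strata, two-sided 0.05. Assumed: exponential times, no dropout, the event-free rates shown, and a log hazard ratio per SD of baseline marker of 0, 0.5, 1.0 or 1.5 (hazard ratios 1, 1.65, 2.72, 4.48). Overall event-free rates were held fixed as prognostic strength varied. The table gives power (%) for the planned stratified log-rank → the score test from a stratified Cox model that also contains the baseline marker, with 1,200 to 1,500 simulated trials per cell.

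| Event-free at Week 26, placebo v KPL-301 | 0 | 0.5 | 1.0 | 1.5 |
|---|---|---|---|---|
| 50% v 85% | 90.7→90.5 | 89.7→91.4 | 91.7→96.5 | 90.9→99.3 |
| 50% v 80% | 77.5→76.9 | 77.9→81.5 | 77.7→89.9 | 77.8→97.3 |
| 50% v 75% | 60.5→60.1 | 61.2→64.7 | 62.4→76.9 | 61.5→87.0 |
| 30% v 65% | 86.0→85.3 | 86.6→90.3 | 88.4→97.5 | 89.7→99.6 |
| 50% v 50% (type I error) | 5.3→5.5 | 4.3→5.1 | 5.1→6.0 | 5.5→5.5 |

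The gain is nil at 0, 1.7 to 3.7 points at 0.5, 4.8 to 14.5 at 1.0, and 8.4 to 25.5 at 1.5.

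**CRP after its exclusion.** Removing the top 10% or 20% of baseline values leaves 63 or 56 subjects. Across 0.5 to 1.5 the gain is 1.4 to 9.8 points at 50% v 85%, and 1.2 to 19.6 points at 50% v 75%. That is smaller than in the full set at 50% v 75% and about the same at 50% v 85%.

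**A separate CRP model.** Here CRP paths were simulated at the ten post-baseline treatment-period visits: baseline below 1.0, geometric mean 0.3, log SD 0.9, drift +0.5 log units, 20% early stopping, 1,000 trials per cell. With a drug effect of −0.6 log units, log-rank v adjusted likelihood-ratio test gave 85.4 v 85.8% at visit-to-visit correlation 0.3, 76.4 v 82.0% at 0.5, and 73.9 v 82.9% at 0.7. At −0.4 the pairs were 54.5 v 56.1, 46.4 v 50.0 and 38.5 v 52.0%. Type I error was 4.8 to 5.6%. All variance components are assumptions.

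**ESR already high at Day 0.** Suppose a fraction f starts at or above 30 and crosses early in both arms (mean 26/12 ≈ 2.2 weeks). Power of the log-rank with everyone kept → with those subjects removed:

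| f | 50% v 85% | 50% v 75% |
|---|---|---|
| 0 | 90.4 | 59.9 |
| 5% | 84.3→89.5 | 52.4→57.5 |
| 10% | 76.3→86.5 | 46.3→56.0 |
| 20% | 56.1→82.2 | 33.7→52.3 |

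**The case against.** A stratified log-rank is a valid prespecified test. Its type I error is right, and chance baseline imbalance is part of that error rate, not a bias. Protocol 14.5.2 assigns these endpoints the primary endpoint's method, and the Amendment 4.0 log says they were added at a regulator's request, so the change is a departure from the protocol. At 50% v 85% the planned test has about 90% power whatever the prognostic strength. All of this stands. It limits the severity but does not remove the gain.

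Two stronger readings are tempting and are not supported. A reader might infer that baseline level largely decides who crosses. No section gives a correlation, variance component or prognostic strength, and at correlation 0.3 the gain was only 0.4 to 1.6 points, within simulation error. A reader might also infer that baseline CRP is ignored altogether and may lie above the threshold in the analysis. SAP 6.7.3.3 excludes those subjects, so only variation below 1.0 mg/dL remains for CRP.

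Two practical objections shape the fix. SAP 6.7.3 uses local CRP for these endpoints, but the Protocol's Table 1 schedules local CRP only at Screening, Day 0 and unscheduled visits, so the ten-visit simulation follows the central CRP schedule. And a covariate model can drop subjects who lack a baseline within 3 days, whom a log-rank would keep.

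**Conclusion.** The point holds as a conditional efficiency loss, not as an error of validity. Neither gated test adjusts for the baseline of the marker that defines its event. Under the assumed strengths, adjustment adds nothing at 0, about 1 to 4 points at a log hazard ratio of 0.5 per SD, 5 to 15 at 1.0 and 8 to 26 at 1.5, with adjusted type I error of 5.1 to 6.0% in the score-test runs.

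ESR is the stronger half: no covariate, no exclusion, and an entry rule that allows ESR of 30 or more at Day 0. With 10% of subjects in that position, power falls from about 90% to 76% at 50% v 85%; removing them restores 86.5%. The documents do not say how many there will be, and the event rates are borrowed from the primary endpoint. These are secondary endpoints in a Phase 2 study, but the sequence passes any loss down to every later test.

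**What to change.** Before unblinding, in SAP 6.7.3.2 and 6.7.3.3:
- Base the gated test (likelihood-ratio p-value) and the hazard ratio on the stratified Cox model with treatment and log baseline ESR, or log baseline CRP, as covariates. Take baseline CRP from the same laboratory source as the endpoint values, and state that source. Keep the stratified log-rank as supportive.
- Exclude from the ESR analysis subjects with baseline ESR of at least 30 mm/hr, matching the existing CRP rule.
- When the 3-day baseline is missing, use the last screening value as the covariate so that no subject is dropped for that reason. It should not trigger the exclusion, because a screening value may date from the active disease required for entry.
- List the change in SAP section 7.

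The cost is SAP text and one extra model term; baseline ESR and CRP are already scheduled. The hazard ratio becomes conditional on baseline level, the gated test departs from the log-rank named in the protocol, and the ESR analysis, like the CRP analysis now, no longer covers the full mITT set.
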